7.2 Statistical Methods

Nonparametric statistics are proposed since it is not known in advance if MoCA scores or levels of neurally-derived exosomes will approximate, or can be transformed, to a normal distribution. A Mann-Whitney U-test will compare exosomal protein levels or MoCA scores between the L-serine treatment and placebo patients at a $p < 0.05$ level. Parametric equivalents will be considered if appropriate to the distribution of the data.

First, we will check the effectiveness of the randomization by comparing the baseline characteristics of the L-serine and placebo groups according to demographic factors (e.g. age, gender). We will also assess whether the levels of biomarkers or cognitive impairment in the treatment group differ from the placebo group at time zero. This first test will check whether the randomization procedures were sufficient for the study. Next we will compare the exosomal protein levels or MoCA scores at the last study visit (month 9). (H_0 = there is no difference between the median exosomal protein level or MoCA score for treatment patients and control patients; H_1 = there is a difference between the median exosomal protein level MoCA score for treatment patients and control patients). A Mann-Whitney U-test will examine exosomal protein levels or MoCA scores of each patient, by comparing median values between groups. Second, we will assess the slope of the exosomal protein levels or MoCA scores over time to see if they differ among the treatment and control groups by Mann-Whitney U-test. We will use Spearman's Rank correlation, in which rho is the equivalent of the parametric correlation coefficient, to determine if there is a monotonic relationship between levels of proteins in the neurally-derived exosomes and the MoCA scores.

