7.1 Sample Size Determination

In a previous study (Fiandaca, 2014), the neurally derived blood exosomal beta-amyloid protein level of eAD patients had a standard deviation of 2.8 pg/ml. The minimum detectable difference in the means of the treatment and placebo subjects is 2.5 pg/ml, with power 0.8 ($\alpha = 0.05$). An increase of approximately 7 pg/ml was observed between preclinical AD and AD patients (Fiandaca, 2014).

Based on Nasreddine et al. (2005), the standard deviation of the MoCA is approximately 4 points. Power calculations suggest that the minimum detectable difference in mean MoCA scores for two groups, each with 20 patients, is 3.65 points. A similar result for sample size comes from Mead's resource equation to predict adequate sample size, e.g. $E = N - B - T$, where N is the required sample size, E is the degrees of freedom of the error component (usually around 20), B is the blocking component for environmental effects, and T is the number of Treatments plus controls,

Placebo: 20 patients

L-serine: 20 patients

Total treatments: 2

Total patients: 40

Subtracting one degree of freedom from each value before inserting it in the equation, we have $E = 39 - 1 - 1 = 37$, Understanding that individual patients may drop out of the study before the 36 week dosing completion for various reasons, this sample size will be adequate to provide the needed statistical power.

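### Section 7.2 judges whether randomization was adequate from a between-arm baseline comparison, which is weak evidence either way; describe baseline, audit the kit allocation, and adjust for the baseline value instead

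*Combined protocol and SAP*

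**What the plan says.** Section 7.2 (Statistical Methods) begins: "First, we will check the effectiveness of the randomization by comparing the baseline characteristics of the L-serine and placebo groups according to demographic factors", with age and gender as examples. It goes on: "We will also assess whether the levels of biomarkers or cognitive impairment in the treatment group differ from the placebo group at time zero". It then states what the comparison is for: "This first test will check whether the randomization procedures were sufficient for the study".

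No test or level is given specifically for the baseline step. The general sentence in the same section reads: "A Mann-Whitney U-test will compare exosomal protein levels or MoCA scores between the L-serine treatment and placebo patients at a $p < 0.05$ level". The alternative hypothesis is two-sided: "H_1 = there is a difference between the median exosomal protein level MoCA score for treatment patients and control patients". The section does not say how large an imbalance would matter, or what follows if the check is passed or failed.

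The efficacy analyses that follow are Mann-Whitney tests of the last-visit value and of the slope over time. Neither is adjusted for a covariate. Section 5.3 describes allocation: the manufacturer randomly assigns kits 1 to 40, 20 to each arm, and the site issues them in number order. No stratification is stated.

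**The concern.** Under the allocation in Section 5.3 the two arms are random halves of one group of patients. If the list was generated at random and followed, the null hypothesis of a baseline test is true by design. A p-value below 0.05 is then a chance finding, not a sign that randomization failed. A p-value above 0.05 with 20 per arm says little about whether the arms are close enough for a fair comparison.

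The plan does more than print a baseline table: it commits to reading adequacy of randomization from the result. Two errors can follow. A sound allocation can be reported as insufficient. Or a chance imbalance in baseline MoCA can be treated as cleared just before week-36 MoCA scores are compared without adjustment for baseline.

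**Working it through.** **Inputs.** From Section 7.1: "the standard deviation of the MoCA is approximately 4 points", and "the minimum detectable difference in mean MoCA scores for two groups, each with 20 patients, is 3.65 points". From Section 7.2: 0.05, two-sided; applying this level to the baseline comparisons is an inference. The variables named are age, gender, MoCA and the biomarker; the demographic list is open-ended.

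**1. The plan's own figure.** For a two-sample t-test with 38 degrees of freedom, SD 4, two-sided 0.05 and power 0.8 (stated for the biomarker, assumed for MoCA), the minimum detectable difference is 3.64 points. Power at 3.65 is 80.3%. The stated 3.65 is reproduced.

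**2. False alarms when randomization is sound.** For k independent tests at 0.05 the chance of at least one significant result is 1 - 0.95^k.
- MoCA and biomarker only: 1 - 0.95^2 = 9.8%.
- All four named variables: 1 - 0.95^4 = 18.5%.
- Four variables with Fisher's exact test for gender, whose actual size here is about 2.1%: 1 - 0.95^3 × (1 - 0.021) = 16.1%. Simulation with three Mann-Whitney tests and one Fisher test gave 15.8%.

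Correlation between the variables would lower these somewhat. Adding variables raises them (six tests, 26.5%).

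**3. Power to see a real difference.** Suppose faulty allocation shifted true mean baseline MoCA by 2 points. The noncentrality is (2/4) × sqrt(20/2) = 1.58, against a critical t of 2.024. Power is 34%, so such a fault would be missed about two times in three.

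**4. Chance gaps that pass.** The standard error of the difference in means is 4 × sqrt(2/20) = 1.265. A gap above 2 points has probability 2 × [1 - Φ(2/1.265)] = 2 × [1 - Φ(1.58)] = 11.4%. In 100,000 simulated sound trials (20 per arm, SD 4, rounded normal scores), a gap above 2 points with a non-significant Mann-Whitney result occurred in about 6.7%.

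**5. What a passed gap does to the unadjusted week-36 comparison.** The documents give no baseline-to-week-36 correlation ρ, so a range is assumed. With equal SDs and a baseline gap D, the expected week-36 difference without any treatment effect is ρD. The chance of a false positive given that gap, by normal approximation, is close to 1 - Φ[(1.96 × 1.265 - ρD) / (1.265 × sqrt(1 - ρ²))]. For D = 2.5, a gap near the edge of significance:

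| ρ (assumed) | Expected bias, points | False-positive rate given the gap |
|---|---|---|
| 0.5 | 1.25 | 13% |
| 0.7 | 1.75 | 21% |
| 0.9 | 2.25 | 34% |

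A gap above 2.5 points is uncommon (4.8% of sound trials), so this table shows the upper end of the problem.

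**6. The slope comparison.** A change from Day 0 subtracts baseline in full, which leaves an expected bias of (ρ - 1)D. At ρ = 0.7 and D = 2.5 that is -0.75 points, against +1.75 for the raw score: smaller, and in the opposite direction.

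**The case against.** The strongest reply is that nothing hangs on the check. Section 7.2 attaches no pass/fail rule, change of test, exclusion or adjustment to it. A reader might infer that a significant result would alter the analysis, or that p > 0.05 formally licenses an imbalance; the text says neither. This stands, and it limits the harm to a wrong stated conclusion and false reassurance.

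Second, a baseline comparison is not empty. The null is true only if the kits were assigned as planned, and a gross allocation failure could show as a baseline difference. This also stands: the check is weak, not meaningless. At 34% power for a 2-point shift it is too weak to support a verdict on the procedures.

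Third, Sections 3.2 and 7.2 also compare slopes, which use each patient's baseline. That is right for the slope analysis, though it over-corrects when ρ is below 1, and it does nothing for the last-visit comparison.

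Fourth, the level for age and gender is inferred, because the 0.05 sentence names only exosomal protein and MoCA. For those two alone the false-alarm figure is about 10%.

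A reader might also go further and say that the check passes every MoCA gap below 2.56 points (2.024 × 1.265), or 70% of the planned effect. The documents do not support that. The 2.56 limit belongs to a t-test with the sample SD at exactly 4. Under the planned Mann-Whitney test, roughly a third of significant results in simulation had smaller gaps. Section 7.1 calls 3.65 a minimum detectable difference, not a planned effect. And the ratio (2.024/2.886 = 0.70) follows from 80% power at almost any sample size, so it shows no special weakness of this trial.

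**Conclusion.** The point holds as a wrong stated inference. A between-arm baseline test cannot carry the conclusion that Section 7.2 draws from it. About 16-19% of sound randomizations would show at least one significant difference if all four named variables are tested at 0.05, and about 10% if only MoCA and the biomarker are. A true 2-point MoCA shift would be found about one time in three. About 7% of sound trials would have a MoCA gap above 2 points that goes unflagged.

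These figures assume 20 evaluable patients per arm, SD 4, roughly normal scores, independent baseline variables and the 0.05 level carried over from the general sentence. The bias figures rest in addition on assumed correlations.

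It would be tempting to conclude that the trial's type I error is inflated. It is not: averaged over randomizations, chance imbalance leaves the overall rate intact. What changes is the error rate given the imbalance that actually occurred, and confidence in the unadjusted week-36 result.

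**What to change.** In Section 7.2:

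1. Delete the sentence that draws a conclusion about randomization from the baseline comparison.
2. Summarize baseline characteristics by arm, including CDR, MoCA and biomarker levels, without significance tests.
3. Verify the conduct of randomization from records: reconcile the kit dispensed to each patient, and the order of issue, with the manufacturer's list and the Investigational Pharmacy's dispensing records (Sections 5.3, 5.8 and 5.9.3). This finds dispensing and sequence errors. It does not show that the list itself was random, so keep the manufacturer's record of how it was generated as well.
4. Pre-specify adjustment of the week-36 MoCA and biomarker comparisons for the baseline value, for example by rank-based ANCOVA, whatever imbalance is observed. Without this step, dropping the tests would leave the week-36 comparison as exposed as before.

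The cost is a few lines of wording, a modest addition to the analysis programs, and one records reconciliation, done after unblinding so that the site stays blinded. No new data are needed: Section 6.1 and the blood-draw schedule in Section 6.9 already provide Day 0 MoCA and exosome samples.

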3.2 Primary Endpoint

This proof-of-concept trial will assess the MoCA score at the week 36 study visit in patients with L-serine treatment compared to placebo. Slopes reflecting the change in MoCA score from Day 0 to the week 36 visit will be compared between treatment and placebo groups.

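### Section 3.2 gives the primary endpoint two MoCA comparisons and no rule for which decides; one should be named, preferably week-36 MoCA adjusted for Day-0 MoCA

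*Combined protocol and SAP*

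**What the plan says.** Section 3.2, headed as the primary endpoint, has two sentences. The first is "This proof-of-concept trial will assess the MoCA score at the week 36 study visit in patients with L-serine treatment compared to placebo". The second is "Slopes reflecting the change in MoCA score from Day 0 to the week 36 visit will be compared between treatment and placebo groups".

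Section 7.2 carries both forward as Mann-Whitney tests at p < 0.05. For the final visit it says "Next we will compare the exosomal protein levels or MoCA scores at the last study visit (month 9", and the hypotheses follow at once: "H_0 = there is no difference between the median exosomal protein level or MoCA score for treatment patients and control patients". It then turns to the other comparison: "Second, we will assess the slope of the exosomal protein levels or MoCA scores over time". It adds that "Parametric equivalents will be considered if appropriate to the distribution of the data". Day-0 MoCA appears in 7.2 only as a check that the arms were alike at the start.

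Section 7.1 sizes the trial on scores: "Power calculations suggest that the minimum detectable difference in mean MoCA scores for two groups, each with 20 patients, is 3.65 points". It accepts that "individual patients may drop out of the study before the 36 week dosing completion for various reasons", without giving a rate.

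Section 3.1 schedules the MoCA at Day 0, week 24 and week 36.

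**The concern.** No sentence says that one MoCA comparison decides, that both are required, or that they are taken in order. The text leans toward week 36: it comes first in 3.2, the hypotheses are attached to it in 7.2, and 7.1 uses the SD of a score. The background in 1.1, however, frames the interest as slower cognitive decline, which suits a slope. The lean does not settle the matter.

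This is a Phase IIa proof of concept looking for a preliminary signal, so what is at stake is readability. If one test is significant and the other is not, the plan gives no way to say what the trial found.

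The second cost is efficiency. The week-36 test makes no use of the Day-0 score. The slope test does use it, but subtracts it in full, which adds noise when the correlation between visits is low.

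**Working it through.** **Inputs from the plan (7.1, 7.2).** SD of MoCA 4; 20 per arm; 3.65 points. Alpha 0.05 and power 0.80 are stated together only for the exosome calculation and are taken to apply to MoCA as well. A two-sided test is inferred from the undirected alternative in 7.2.

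**Assumed, not in the documents.** Correlation r between visits of 0.3 to 0.9; equal SDs; mean MoCA 20; no dropout unless stated; 2.5 points as a second effect size.

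**Step 1: the plan's figure.** A two-sample t-test (noncentral t, SD 4, 20 per arm, 80% power) detects 3.64 points, against the stated 3.65. Power at 3.65 is 80.3%. The figure therefore belongs to an unadjusted comparison of scores with nobody lost. With 18 per arm the detectable difference becomes 3.85 and power at 3.65 falls to 76%.

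**Step 2: detectable difference by analysis.** It scales with the SD: 3.64/4 = 0.91 points per unit of SD. The SD is 4 for the score, 4 × sqrt(2(1 − r)) for the change from Day 0, and 4 × sqrt(1 − r²) for week 36 adjusted for Day 0. At r = 0.5 these are 4.00, 4.00 and 3.46.

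| r | 0.3 | 0.5 | 0.7 | 0.8 | 0.9 |
|---|---|---|---|---|---|
| Week-36 score | 3.64 | 3.64 | 3.64 | 3.64 | 3.64 |
| Change from Day 0 | 4.30 | 3.64 | 2.82 | 2.30 | 1.63 |
| Week 36 adjusted for Day 0 | 3.47 | 3.15 | 2.60 | 2.18 | 1.59 |

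Which of the two planned comparisons is stronger reverses at r = 0.5.

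**Step 3: simulation of the planned tests.** 20,000 trials per cell, whole-number scores limited to 0-30, visits at weeks 0, 24 and 36, effect growing linearly. The plan does not say whether the slope uses week 24; here it does. The adjusted analysis is analysis of covariance (ANCOVA).

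| r | 0.3 | 0.5 | 0.7 | 0.8 | 0.9 |
|---|---|---|---|---|---|
| No effect: either test significant, % | 8.8 | 8.9 | 9.4 | 9.3 | 9.3 |
| 3.65 points: slope power, % | 64 | 78 | 94 | 99 | 100 |
| 3.65 points: both significant, % | 56 | 64 | 74 | 77 | 77 |
| 3.65 points: tests disagree, % | 31 | 27 | 24 | 23 | 23 |
| 3.65 points: ANCOVA power, % | 83 | 89 | 97 | 99 | 100 |
| 2.5 points: slope power, % | 35 | 46 | 67 | 84 | 98 |
| 2.5 points: ANCOVA power, % | 51 | 59 | 75 | 88 | 99 |

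The week-36 score test has 77-78% power at 3.65 points and about 46% at 2.5 points, whatever r is. Each planned test alone has about 5% false positives. Repeat simulations put disagreement at 22-31%. Varying the mean (16, 20, 24) and letting the correlation decay with time widens that to 22-35%, with either-test false positives of 8.2-9.6%.

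**Step 4: direction of disagreement.** At r = 0.8 it is score-only in 1% of trials and slope-only in 22%; at r = 0.3 it is 22% and 8%. Away from r = 0.5 it runs mostly toward the more powerful test. At r = 0.5 the two powers are equal and the split is about even (78 − 64 = 14 each way).

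**Step 5: permutation p-value for the adjusted difference.** In 3,000 trials of 999 permutations, type I error was 4.4-5.7% and power at 2.5 points was 51/59/74/88/99%.

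**Step 6: departure from normality.** An assumed 15% of patients in both arms lose 6-12 points, with a 2.5-point effect and r (before that decline) of 0.7/0.8/0.9. Power is 45/56/81% for the slope test and 41/46/53% for ANCOVA. With 10% losing 5-10 points it is 54/66/88% against 55/63/73%. With 15% losing 4-8 points it is 52/64/84% against 56/64/75%. Against the unadjusted week-36 test, the adjusted analysis was about equal or better in every such scenario tried.

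**Step 7: the open parametric option.** Taking the smaller of the Mann-Whitney and t-test p-values at week 36 gives 5.7-6.0% false positives, a minor matter.

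**The case against.** The strongest reply is that naming either planned test would remove the ambiguity in one sentence, and that 7.2 nearly does so by attaching the hypotheses to the last visit and calling the slope second. On this view, replacing both tests with a third is an efficiency preference that depends on a correlation the documents do not give. That stands in part: the need for one named analysis and the choice of analysis are separate, and only the first follows from the text.

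It is also fair that disagreement is not an error rate. At high correlation it is mostly two tests of unequal power, not contradictory evidence.

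Two stronger readings are tempting, and neither is supported. A reader might infer that the trial runs a false-positive risk of about 9%. That needs a rule that either result counts, and the plan states none; with one deciding test the risk is about 5%. A reader might also infer that baseline adjustment is always the most powerful choice. That holds for near-normal scores only. Section 7.2 chose rank tests because normality was not assured, and with fast decliners and high correlation the planned slope test can win clearly (81% against 53% at r = 0.9 in Step 6). The permutation p-value protects type I error but does not restore that power.

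**Conclusion.** The point holds as a matter to fix. The primary endpoint contains two MoCA tests, the text leans toward week 36, and nothing says which decides. At 3.65 points the two would disagree in about 22-31% of trials, assuming near-normal scores, r of 0.3 to 0.9 and no dropout. The consequence is an unclear signal in a proof-of-concept trial, not a wrong confirmatory claim.

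That the deciding test is unnamed is certain from the documents. The preference for baseline adjustment is a recommendation. It keeps the time point toward which the text leans, uses a score already collected and, under near-normal scores, is at least as powerful as both planned tests. Its gain at 2.5 points is small over the score test at low r (51 − 46 = 5 percentage points at r = 0.3) and small over the slope test at high r (99 − 98 = 1 at r = 0.9).

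How missing week-36 scores are handled is a separate question and does not affect this conclusion.

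**What to change.** In 3.2 and 7.2, name one deciding MoCA analysis and label the others supportive. The recommended choice is week-36 MoCA compared between arms with Day-0 MoCA as covariate. Report the adjusted difference with its 95% CI and a pre-specified permutation p-value for the same statistic, permuting in the way allocation was actually done. This replaces the open choice of parametric methods. Keep the Mann-Whitney slope comparison as a pre-specified supportive analysis, with the unadjusted week-36 Mann-Whitney test beside it. State the downsides in the plan: a linear baseline relation is assumed, the gain is small at some correlations, and power may be lost to the slope test if a minority decline fast. In 7.1, label 3.65 points as the unadjusted t-test figure with no dropout.

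Fix this before any outcome data are viewed by arm. Tying it to unblinding would be too late, because 6.8 places unblinding after the final analysis. If outcomes have already been seen by arm, report the adjusted analysis as post hoc.

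The cost is a protocol amendment to 3.2, 7.1 and 7.2, submitted to the ethics committee or IRB as Section 10 requires. No new assessments or patients are needed.

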At week 24 and week 36, we propose to utilize a portion of the blood sample to examine neurally derived blood exosomes as potential biomarkers. Exosomes are a class of endosome-derived membrane vesicles which are shed by neural cells and transported in blood plasma. Thus, they provide an accessible measure of proteins excreted by neuronal cells. Since two proteins, phosphorylated tau and beta-amyloid-42, are implicated in the formation of neurofibrillary tangles and amyloid plaques, they can potentially be used as biomarkers of disease status. Fiandaca et al. (2015) found that the concentrations of phosphorylated tau and beta-amyloid present within exosomes were significantly higher for AD patients than case controls and that they increased progressively with time and disease progression. We propose to examine, in this proof-of-concept trial, if these exosome biomarkers change as a result of L-serine treatment. Furthermore, we will assess whether the concentrations or presence of these biomarkers show any correlation with cognitive decline.

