3.3 Secondary Endpoints

The Institute of Ethnomedicine will also assess plasma neurally derived exosome protein levels of beta-amyloid, as a biomarker which may be related to cognitive decline in eAD (Fiandaca et al. 2015). Slopes reflecting the change in biomarker protein level will be compared between treatment and placebo groups. In addition, we will assess the relationship between the MoCA scores and the concentration of plasma neuronal derived exosome biomarkers (Fiandaca et al. 2015) to demonstrate that this biomarker is related to cognitive decline, and that the MOCA assessment and neural exosome biomarkers are useful for future studies.

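### The only planned biomarker–MoCA association test is cross-sectional, so by itself it cannot support the conclusion about cognitive decline sought in sections 3.1 and 3.3

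*Combined protocol and SAP*

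**What the plan says.** Section 3.1 states the aim: "we will assess whether the concentrations or presence of these biomarkers show any correlation with cognitive decline". Section 3.3 has two parts. The operational clause is "we will assess the relationship between the MoCA scores and the concentration of plasma neuronal derived exosome biomarkers"; the purpose attached to it is "to demonstrate that this biomarker is related to cognitive decline", and to show that both measures are useful for later studies.

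Section 7.2 gives one association analysis, a Spearman rank correlation "to determine if there is a monotonic relationship between levels of proteins in the neurally-derived exosomes and the MoCA scores". It does not name the visit, say whether repeated visits enter, or say how treatment arm is handled. Slopes of both measures are planned, but only for a Mann-Whitney comparison of L-serine with placebo. No analysis relates a patient's MoCA change to that patient's biomarker change or biomarker level.

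**The concern.** Decline is change within a patient over time. A correlation between protein level and MoCA score at a visit asks a different question: whether patients with higher levels also have lower scores. Patients can differ stably on both measures without the two moving together, and the two can move together without any baseline association. The planned test can therefore be significant when changes are unrelated, and can miss changes that are related.

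At stake is the inference in 3.3. If that conclusion is drawn from the level–score result alone, later trials could adopt the biomarker as a marker of progression, or drop it, on evidence that does not address progression.

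**Working it through.** **The plan's own figures.** Section 7.1 gives SDs of 2.8 pg/ml (exosomal beta-amyloid) and about 4 points (MoCA), with 20 patients per arm. For two means, the minimum detectable difference is SD × √(2/n) × (1.96 + 0.842).

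- Beta-amyloid: 2.8 × 0.3162 × 2.802 = 2.48 pg/ml (2.55 with the t distribution); stated 2.5.
- MoCA: 4 × 0.3162 × 2.802 = 3.54 points (3.64 with t); stated 3.65.

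Both reproduce. They concern differences between arms; the documents give no figure for the correlation.

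**What a week-36 level–score correlation contains.** Let ρ0 be the baseline correlation, ρc the correlation of the changes, and k the SD of change divided by the between-patient SD (the same for both measures), with change independent of baseline. Then

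correlation at week 36 = (ρ0 + k²ρc) / (1 + k²).

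With k = 0.5 this is 0.8ρ0 + 0.2ρc.

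- ρ0 = -0.5, ρc = 0: -0.40, although the changes are unrelated.
- ρ0 = -0.3, ρc = 0: -0.24.
- ρ0 = 0, ρc = -0.5: -0.10, although the changes are related.

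The two-sided 5% critical value of Spearman's rho at N = 40 is about 0.31.

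**Simulation.** From the documents: SDs of 2.8 and 4, and N = 40. Assumed, because the documents are silent: ρ0, ρc, SD of change 1.4 pg/ml and 2 points (k = 0.5), mean changes +1 and -1, and N = 32 as an illustration of 20% loss. MoCA was rounded to whole points and limited to 0–30. Each scenario had 20,000 or more simulated trials, tested two-sided at 0.05.

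| ρ0 | ρc | N | Level–score, week 36 | Change–change |
|---|---|---|---|---|
| 0 | 0 | 40 | 5% | 5% |
| -0.3 | 0 | 40 | 29% | 5% |
| -0.5 | 0 | 40 | 69% | 5% |
| 0 | -0.5 | 40 | 9% | 87% |
| -0.3 | 0 | 32 | 24% | 5% |
| -0.5 | 0 | 32 | 59% | 5% |
| 0 | -0.5 | 32 | 8% | 78% |

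Repeat runs differ by about one percentage point (for example 30%, 68% and 88% in rows two to four).

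**Sensitivity.** At ρ0 = -0.5, ρc = 0 and N = 40, the level–score rate is about 79% when k is about 0.36 and about 32% when k = 1.

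**Precision of the added analysis.** By Fisher's z with SE = 1.03/√(n - 3) = 1.03/√37 = 0.169, an observed rho of 0.4 has z = 0.424 ± 1.96 × 0.169. The 95% CI is about 0.09 to 0.64.

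**The case against.** The strongest reply is that 7.2 does what 3.3 asks. The operational clause of 3.3 relates scores to concentration, and the Spearman test is exactly that. This stands. A reader might infer that 7.2 contradicts the secondary endpoint; it does not. The gap lies between that analysis and the conclusion 3.3 draws from it, and between 7.2 and the aim sentence in 3.1.

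Decline might be read loosely as current impairment, which would narrow the gap. But section 3.2 measures the primary outcome partly by slopes of MoCA change, and 3.1 speaks of biomarkers rising as disease progresses, so the longitudinal reading is the natural one. Nor does 7.2 test the literal reading of 3.1, in which biomarker concentration is related to decline.

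It would be too strong to say that the level–score correlation says nothing about decline. A week-36 value contains baseline plus change; in the example above the change correlation enters with weight 0.2.

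The 29% and 69% are also not false-positive rates of the test as specified. They are its power to detect a cross-sectional correlation that was assumed, and with none assumed the rate is 5%. They become misleading only if a significant result is reported as evidence about decline.

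A reader might further infer that visits or arms will be pooled and the p-value distorted. Section 7.2 neither states nor excludes this, so it is a missing detail and no error rate can be charged to the plan. Finally, 3.3 does not speak of validating the biomarker.

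**Conclusion.** The concern holds in limited form. The planned Spearman test fits the operational clause of 3.3 but is cross-sectional, and no planned analysis links either measure to a patient's MoCA change. It cannot by itself support a conclusion about decline.

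The size depends on a baseline correlation and SDs of change that the documents do not give. With k = 0.5, N = 40 and unrelated changes, the chance of a significant result runs from 5% to about 69% as the baseline correlation goes from 0 to -0.5. For related changes without a baseline correlation, the test has little power (about 9%, against 87% for change versus change).

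This is one secondary analysis in a proof-of-concept trial, and a cheap improvement. It does not touch the primary MoCA comparison or safety.

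**What to change.** In section 7.2:

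- Add a Spearman correlation of each patient's biomarker slope with the same patient's MoCA slope, Day 0 to week 36, one pair per patient. Calculate slopes from actual sampling dates, since 6.9 allows blood draws to be delayed.
- Add a Spearman correlation of baseline biomarker level with MoCA slope, to cover the literal wording of 3.1.
- Report rho with a 95% CI for each, both overall and adjusted for arm. The overall estimate includes co-movement driven by treatment; the adjusted one removes it.
- Keep the level–score correlation at one named visit, label it cross-sectional, and do not base the 3.3 conclusion about decline on it.

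Reconcile the exosome visits first. Section 3.1 names weeks 24 and 36, section 6.1 includes baseline, section 6.9 lists all four visits, and the week 12 list in 6.5 omits exosomes. A Day 0 to week 36 slope needs the baseline sample confirmed.

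The cost is wording: MoCA is scheduled at Day 0, week 24 and week 36, and sections 6.1, 6.6 and 6.7 schedule exosome samples at the same visits. The downside is imprecision. An observed rho of 0.4 at n = 40 has a CI of about 0.09 to 0.64. A true correlation of 0.3 would be detected only about 45% of the time (atanh 0.3 = 0.310; 0.310/0.169 - 1.96 = -0.13), so a non-significant slope correlation should not be read as showing no relation.
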